## 1 STUDY DESCRIPTION

### 1.1 History/Rationale

SNM is a well-established therapy for subjects with Urinary and Fecal dysfunction. To date, over 200,000 subjects worldwide have received InterStim® SNM implants.

In 1994, Medtronic obtained CE Marking for SNM for the management of chronic intractable disorders of the pelvis and lower urinary or intestinal tract and is currently the only company marketing this therapy. The device has proven to be safe and effective (see Section 1.2 below), however, improvement in technology could potentially improve the subject experience, reduce costs to the healthcare system and expand access to the therapy.

Medtronic's implantable neurostimulator employs a primary cell battery that requires the device be explanted and replaced on average, every 3-5 years. Additionally, the InterStim neurostimulator uses constant-voltage therapy that does not provide a fixed amount of current as the tissue impedance changes, requiring an adjustment of stimulation amplitude over time to maintain efficacy.

The Axonics SNM System addresses these shortcomings based on the following innovations and improvements:

- A rechargeable battery: The battery inside the Axonics neurostimulator is qualified to last at least 15 years, obviating the need for recurring surgical explants and replacements.
- A smaller neurostimulator size: The Axonics neurostimulator is 5.5 cc, which is 60% smaller than the InterStim neurostimulator, which may improve patient comfort.
- Current-controlled stimulation: The Axonics neurostimulator automatically adjusts output voltage based on tissue impedance, which may provide a more consistent therapy and may reduce the need for stimulation adjustments by the subject and/or physician.

While none of these advancements are expected to modify therapy, it is hypothesized that they may reduce adverse events, lower the risk profile and improve the patient experience.

### 1.2 Previous Clinical Studies

A recent guidance document by the American Urological Association provides an extensive and systematic literature review on SNM. The guidance stated, “Given the negative effects on quality of life associated with severe incontinence and frequency, the panel judged that benefits of SNM in the appropriate patient outweighed the risks/burdens and notes that patients should be carefully

---

 Gormley, E. A., Lightner, D. J., Burgio, K. L., Chai, T. C., Clemens, J. Q., Culkin, D. J., Vasavada, S. P. (2014). Diagnosis and treatment of overactive bladder (non-neurogenic) in adults: AUA/SU FU guideline. Retrieved from <https://www.auanet.org/common/pdf/education/clinical-guidance/Adult-Urodynamics.pdf>.

counseled regarding the risk/burdens."

The adverse event profile for SNM therapy has been determined to be acceptable. Moreover, the InSite study shows that improvements in implantation technique and the introduction of a smaller neurostimulator and Tined Lead in recent years have led to lower adverse event rates.

To date, the Axonics SNM System was implanted in fifty-one (51) European subjects with symptoms of Overactive Bladder (OAB), including UUI, and urgency-frequency alone or in combination with UUI, in the RELAX-OAB study, a multi-center, prospective, post-market clinical follow-up study.

The 3-month follow-up results of the study indicate that the outcomes and safety profile of the Axonics SNM System are comparable to the InterStim device.

### **1.3 Purpose**

The ARTISAN-SNM study is a pivotal study designed to evaluate the safety and effectiveness of the Axonics Sacral Neuromodulation System as an aid in the treatment of the symptoms of UUI designed to gain pre-market approval in the United States.

The secondary objectives of the ARTISAN-SNM study are to evaluate the technical performance, health economics of the Axonics SNM System, and quality of life of patients as an aid in the treatment of the symptoms of UUI.

Given the Axonics SNM System has CE Mark approval, the ARTISAN-SNM study is considered a post-market clinical follow-up study for the European Union (EU).

### **1.4 Safety**

All adverse events will be recorded. All reported adverse events will be graded using the Clavien-Dindo classification of surgical complications or Common Terminology Criteria for Adverse events (CTCAE), and adjudicated by an independent DSMB committee. Adverse events will be classified based on seriousness and relatedness ('related' or 'not related') to the subject's device.

The definition of adverse events classified as Serious adverse events is provided in Section 8.6.1. Specifically, the number of events and subject rates of the following will be tabulated and reported:

- Adverse device effects (ADEs)
- Adverse procedure effects (APEs)
- Serious adverse events (SAEs)
- Serious adverse device effects (SADEs)
- Unanticipated adverse device effects (UADEs)

---

## 1.5 Effectiveness Endpoint

The primary effectiveness endpoint is defined as the percent of all implanted subjects who have 50% or greater reduction in the number of urgency leaks at six (6) months (*Details in Section 5.2.3.1*).

The following metrics will also be measured according to the study schedule in Table 1:

- Device performance metrics
- Leaks and voids per day with associated urgency and leak magnitude (72-hour voiding diary)
- Quality of life questionnaires (EQ-5D, ICIQ-OABqol)
- Subject satisfaction with treatment
- Bowel function questionnaires (CCF-FIS, CCCS)
- Medication usage
- Healthcare utilization

## 1.6 Study Justification

The study will be a prospective, multi-center, single-arm pivotal study. Subject outcomes will be compared to their baseline, with subjects serving as their own control. This study will use a performance goal as the primary endpoint metric.

Based on the evaluation of pre-clinical data, risk analysis and that SNM is a well-established therapy, a single-arm study should be sufficient to evaluate the safety and effectiveness of the device. As noted in a recent review, numerous studies have been conducted on SNM therapy, including randomized, controlled studies, and this study is expected to provide clinical data comparable to published results.

The study is anticipated to begin enrollment in the second half of 2017 and is expected to complete enrollment within 12 months. The study will be conducted at a maximum of twenty (20) centers in the United States, Canada, and Western Europe. The scheduled visits are shown in the Study Schematic (Figure 1) and Visit Schedule (Table 1). Subjects will be permitted unscheduled follow-ups as needed.

Study sites and investigators will be selected according to the Axonics Site Selection Standard Operating Procedure. They will be selected based on their experience with SNM therapy and their ability to conduct clinical research. At least half of the study sites will be located in the United States to ensure that the outcomes are reflective of the U.S. patient experience.

Reports will be prepared when all subjects reach the primary endpoint, and after the all study subjects have completed their final study visit.

An independent Data Safety Monitoring Board will assess the safety of the device as the study progresses.

---

 Gormley, E. A., Lightner, D. J., Burgio, K. L., Chai, T. C., Clemens, J. Q., Culkin, D. J., Vasavada, S. P. (2014). Diagnosis and treatment of overactive bladder (non-neurogenic) in adults: AUA/SUFU guideline. Retrieved from <https://www.auanet.org/common/pdf/education/clinical-guidance/Adult-Urodynamics.pdf>.

### *1.6.1 Intraoperative Test*

Per standard SNM procedure, subjects will undergo an intraoperative test to ensure that good motor thresholds are observed from at least two (2) electrodes. If two (2) electrodes produce a satisfactory response, then the subject will be implanted with the Axonics Tined Lead and Neurostimulator (full system implant).

### *1.6.2 External Trial in Commercial Setting*

In a typical commercial setting, patients undergo a surgical procedure to implant a trial lead, which is externalized through the skin and connected to an external stimulator that is worn on the patient's waist. The external trial period can last up to one month, at the end of which subjects who experience  $\geq 50\%$  reduction in symptoms are determined to be "Trial Responders" and undergo a second surgical procedure to have a full system implanted. Patients that do not respond to external trial stimulation are determined to be "Trial Non-responders", and undergo a second procedure to have the lead surgically removed and the external stimulator disconnected.

### *1.6.3 Trial Period in ARTISAN-SNM Study*

In the ARTISAN-SNM study, subjects will not undergo "external trial stimulation".

In the ARTISAN-SNM study, subjects will be classified as Trial Responders or Trial Non-responders based on whether or not they have  $\geq 50\%$  reduction in symptoms during the first one-month Trial period.

As is the case in SNM clinical literature and to allow for clinically relevant interpretation of study outcomes, a secondary effectiveness outcome will be performed for subjects classified as Trial Responders.

Forgoing the external trial stimulation period will reduce the number of procedures for the vast majority of subjects. Because the lead is not externalized for the trial period, it is hypothesized that the infection rate will be decreased.

## 2 STUDY DEVICE

Axonics SNM Therapy for urinary control is CE Marked and indicated for the treatment of fecal incontinence, urinary retention and the symptoms of overactive bladder, including UUI and significant symptoms of urgency-frequency alone or in combination, in patients who have failed or could not tolerate more conservative treatments. The Axonics SNM System does not have marketing approval in the U.S.

The Axonics SNM System, as illustrated in Figure 2, is comprised of the following devices:

- i. Neurostimulator: rechargeable implanted device that provides electrical pulses to stimulate the target sacral nerve.
- ii. Tined lead: a tined lead with four (4) electrode contacts to provide stimulation. The distal tip is implanted through the applicable foramen near the S3 sacral nerve with the proximal end connected to the Neurostimulator. Tines on the lead facilitate fixation of the lead just posterior to the sacral foramen.
- iii. Remote control (RC): a non-rechargeable battery-powered device that uses radio-frequency (RF) signals to communicate with the Neurostimulator. The RC allows the subject to check and adjust the stimulation level, to check the status of the Neurostimulator battery charge level and to turn stimulation on or off.
- iv. Charger: a portable device powered by a rechargeable battery. The Charger is used for transcutaneous charging of the Neurostimulator through RF induction.
- v. Dock: a device that connects to a wall outlet and is used to recharge the Charger.
- vi. Clinician programmer (CP): a tablet computer used by a clinician or Axonics Representative to program the Neurostimulator.

The following surgical tools that are required for implantation are also part of the Axonics SNM System:

- vii. Foramen needle with needle stylet: used for locating the correct sacral foramen for implant and subsequent acute stimulation testing.
- viii. Directional guide: a thin metal rod that holds the position in the sacral foramen as determined by using the foramen needle for the subsequent placement of the introducer sheath and dilator.
- ix. Introducer sheath and dilator: tool that increases the diameter of the hole through the foramen to allow introduction of the Tined Lead.
- x. Lead stylet (straight or curved tip): a stiff wire that is inserted into the lead to increase its stiffness during lead placement.
- xi. Torque wrench: a small wrench used to tighten the setscrew that locks the lead with the Neurostimulator.
- xii. Tunneling tool: a stiff, sharp device that creates a subcutaneous tunnel, allowing the lead to be placed along a path under the skin.
- xiii. Needle stimulation cable: a cable provided to connect the CP to foramen needle to

deliver test stimulation during lead placement procedure.

xiv. Lead stimulation cable: cable provided to connect the CP to Tined Lead to deliver test stimulation during lead placement procedure.

**Figure 2: The Axonics SNM System**

Please see the device manuals for additional information on the device(s) and their use.

All implantable components and surgical tools are single use only. There will be no re-sterilization and no re-use of these components.

### 3 STUDY POPULATION

Subjects will be recruited from each investigator's patient population. The investigator has the responsibility of screening potential subjects and selecting those who meet the eligibility criteria for the study. A screening form will be filled out by the physician prior to enrolling the subjects, based on the subject's chart review. Candidates will be enrolled in the study only after having met all the inclusion and none of the exclusion criteria, and having given their informed consent.

Subjects who are enrolled in ARTISAN-SNM will be given a subject identification card. The subject should present this card to all active healthcare providers to ensure subject safety and compliance with the ARTISAN-SNM protocol.

#### 3.1 Inclusion Criteria

The following are the inclusion criteria for the study:

**Inclusion Criteria:**

Diagnosis of UUI demonstrated on a 72-hour voiding diary defined as:

- a minimum of four (4) leaking episodes associated with urgency,
- at least 50% of all leaking episodes associated with urgency, and
- at least one leaking episode each 24-hour period.

Greater than or equal to 6 months' history of UUI diagnosis

For male subjects only:

- Peak flow rate > 15 cc/s as verified by uroflowmetry within 6 months prior to enrollment
- Residual bladder volume < 150 cc tested within 6 months prior to enrollment

Positive motor response on at least two (2) implanted electrodes during intraoperative test in the S3 (preferred) or S4 foramen

21 years of age and older

For patients' over 70 years of age, or any patient at the discretion of the Investigator, Edmonton Frail Scale score of 9 or less

Failed conservative therapy and second-line drug therapy and is not a candidate for additional conservative or second-line therapy

No changes to current regimen of medications that affect bladder function for at least four (4) weeks prior to beginning the baseline voiding diary and baseline questionnaires

Willing and capable of providing informed consent  
Capable of participating in all testing associated with this clinical investigation

### 3.2 Exclusion Criteria

Subjects who meet any one of the following criteria will be excluded from this clinical investigation:

**Exclusion Criteria:**

- More than minimal level of stress incontinence or mixed incontinence with stress component likely to confound study outcome.
- Current urinary tract mechanical obstruction (e.g. benign prostatic enlargement or urethral stricture)
- Interstitial cystitis or bladder pain syndrome as defined by either AUA or EAU guidelines
- Chronic pelvic pain
- History of any pelvic cancer
- Uncontrolled hypertension
- Any significant medical condition that is likely to interfere with study procedures, device operation, or likely to confound evaluation of study endpoints (e.g. Crohn's disease, moderate to severe fibromyalgia, chronic pain, etc.)
- Any psychiatric or personality disorder at the discretion of the study physician
- PHQ-15 score of  $\geq 15$
- Current symptomatic urinary tract infection (UTI) or more than three (3) UTIs in past year
- Any neurological condition that could interfere with normal bladder function, including stroke, epilepsy, multiple sclerosis, Parkinson's disease, clinically significant peripheral neuropathy, or spinal cord injury (e.g., paraplegia)
- Uncontrolled diabetes (A1C  $> 6.5$ , documented in the last three (3) months)
- Diabetes with peripheral nerve involvement
- Treatment of urinary symptoms with botulinum toxin therapy within twelve (12) months prior to SNM implant date

Treatment of urinary symptoms with tibial nerve stimulation within three (3) months prior to SNM implant date

Previously implanted with a sacral neuromodulation device

Underwent an external trial and was deemed a non-responder

Pelvic organ prolapse stage 3 or higher

History of pelvic floor surgery, including surgical treatment for stress incontinence or prolapse, within 6 months prior to SNM implant date

Surgical treatment for stress incontinence (sling, Burch or urethral injection) or pelvic organ prolapse recommended or planned at enrollment

History of allergic response to titanium, zirconia, polyurethane, epoxy, or silicone

Knowledge of planned MRIs on areas other than the head, diathermy, or high output ultrasonic exposure

Any other active implanted devices (e.g., drug delivery pumps, pacemaker, ICD) including neurostimulators whether turned on or off. Passive implants (e.g., prostheses) are allowed, but no implanted metal should be at the Neurostimulator implant site

A female who is breastfeeding

A female with a positive urine pregnancy test

Currently participating in another clinical trial

### 3.3 Subject Disposition

#### 3.3.1 Enrolled Subjects

Subjects who have signed the informed consent form will be considered enrolled in the study and will count towards the Enrollment Cap.

#### 3.3.2 Pre-operative Screen Failures

A subject who has signed the informed consent, is found to not meet the inclusion/exclusion criteria and will not undergo the implant procedure with the device. Subject will be classified as a "Screen Failure." Any adverse events from the signing of the informed consent to the point of screen failure will be recorded, but no further follow-up will be required. The original signed Informed Consent and any associated adverse event forms will be maintained in the center's administrative file. All open adverse events should be followed until closed or documented as chronic.

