## STUDY SYNOPSIS

Study Title:	Axonics Sacral Neuromodulation System for Urinary Urgency Incontinence Treatment: ARTISAN-SNM
Study Device:	Axonics Sacral Neuromodulation System (SNM) System
Study Design:	Single-arm, prospective, multi-center, unblinded pivotal study
Indication for Use:	Axonics Sacral Neuromodulation Therapy for Urinary Control is indicated for the treatment of the symptoms of Urinary Urgency Incontinence (UUI) in patients who have failed or could not tolerate more conservative treatments.
Primary Objective:	To evaluate the safety and effectiveness of the Axonics Sacral Neuromodulation System as an aid in the treatment of the symptoms of UUI designed to gain pre-market approval in the United States.
Secondary Objective:	To evaluate the technical performance and health economics of the Axonics SNM System and the quality of life of patients in the treatment of the symptoms of UUI.
Subjects:	Up to one hundred and forty-five (145) subjects enrolled or at least one hundred and sixteen (116) implanted subjects
Centers:	Up to 20 centers (U.S., Canada, and Western Europe)
Study Duration:	The study duration is expected to be approximately 36 months. The enrollment phase will be approximately 12 months. Subjects will participate in the study for 24 months post activation.
Primary Effectiveness Endpoint:	Proportion of all implanted subjects that are Treatment Responders (i.e. subjects with $\geq 50\%$ reduction in the number of urgency leaks) is greater than 50% at 6-months post activation.
Secondary Endpoints:	The following secondary endpoints are planned in all implanted subjects at 6-month follow-up 

• Improvement from baseline in ICIQ-OABqol total score (HRQL)

- Reduction from baseline in average daily number of urgency leaks
- Reduction from baseline in average daily number of large urgency leaks
- Reduction from baseline in average daily urgency
- Improvement from baseline in average daily number of voids

Additionally, the following endpoint is planned in Trial Responders cohort at 6-month follow-up:

- Responder rate

**Primary Safety Endpoint:** Rate of adverse events (AEs) at 6 months post-activation

**Safety Measures:** Adverse device effects (ADEs)

Adverse procedure effects (APEs)

Serious adverse events (SAEs)

Serious adverse device events (SADEs)

**Performance Measures:** Device performance metrics

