### *3.3.3 Intraoperative Screen Failures*

A subject who has signed the informed consent, in whom the implant procedure is initiated, and does not meet the intraoperative inclusion criteria will not be implanted with the Axonics SNM System. If the subject is not implanted, the subject will be classified as an “Intraoperative Screen Failure” and will be managed according to section 3.3.2.

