#### *5.2.3.1 As-Treated*

The primary endpoint As-Treated analysis will include subjects implanted with the Axonics SNM that have data available. Additionally, implanted subjects with missing data, or subjects that are intraoperative screen failures, will also be included in this analysis, and their data will be imputed based on the circumstance of the missing data. Details on Missing data imputation are provided in Section 11.4.

Adverse event data will be based on all implanted subjects and intra-operative screen failures. Pre-operative screen failures will be excluded from all analyses, and will be presented separately.

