#### *5.2.3.2 Per Protocol*

The per protocol analysis set will include all subjects in the As-Treated set that have no major protocol deviations (e.g., failed intraoperative testing but was implanted) that would potentially affect study outcomes.

Screen failures will be excluded from effectiveness analyses, and will be presented separately.

All safety data will be summarized and analyzed based on all implanted subjects and intraoperative screen failures.

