### *5.2.4 Analysis methods*

#### *5.2.4.1 Primary Endpoint*

The primary effectiveness endpoint is that the proportion of all implanted subjects that are Treatment Responders is greater than 50% at 6-months post-activation. If the proportion of Treatment Responders is statistically greater than 50%, the study will be considered to be a success.

As mentioned above, a secondary endpoint analysis will also be conducted in subjects who are "Trial Responders" to allow for a direct comparison to the published SNM literature where analysis at follow-up visits are performed only in trial responders i.e. subjects that have  $\geq 50\%$  improvement in

symptoms after a one-month trial with an external stimulator.

The primary endpoint will be tested for significance based on a one-sided binomial test (such as Fisher's exact test) at a 2.1% significance level to account for two additional early looks as detailed in the Statistical Analysis Plan.

The primary safety endpoint of the study is the rate of adverse events (AEs) through 6-months.

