### 8.6.1 Adverse Event Classification

**Adverse Event (AE)** – any untoward medical occurrence, unintended disease or injury, or untoward clinical signs (including abnormal laboratory findings) in subjects, users or other persons, whether or not related to the investigational medical device. This definition includes events related to any procedure in the protocol. The following are NOT considered AEs:

1. Any event expected to occur during the normal course of treatment that is not untoward.
2. Usual aches and pains following the surgical implant procedure. (Pain that is unusually intense or prolonged may be an AE.)
3. Unusual or uncomfortable sensations during the programming of the device or when the Remote Control is used to change stimulation settings. These occurrences are part of the usual standard of care. If the sensation is not resolved by reprogramming then the event may be considered an AE.
4. Change in the effectiveness of the SNM therapy may change over time, possibly requiring changes in programming parameters.
5. Underlying diseases, recorded at baseline, unless there is an increase in severity or frequency during the course of the investigation.
6. Death should not be recorded as an AE, but should only be reflected as an outcome of a specific SAE.

Any AE experienced by the study subject after informed consent, whether before, during or subsequent to the procedure, must be recorded in the eCRF.

**Adverse Device Effect (ADE)** – adverse event related to the use of an investigational medical device.

- a) This definition includes adverse events resulting from insufficient or inadequate instructions for use, deployment, implantation, installation, or operation, or any malfunction of the

investigational medical device.

- b) This definition includes any event resulting from use error or from intentional misuse of the investigational medical device.

**Serious Adverse Device Effect (SADE)** – An effect that has resulted in any of the consequences characteristic of a serious adverse event related directly to the investigational medical device.

**Serious Adverse Event (SAE)** – adverse event that:

1. Led to death
2. Led to serious deterioration in the health that either resulted in
  - a. a life-threatening illness or injury, or
  - b. a permanent impairment of a body structure or a body function, or
  - c. In-patient or prolonged hospitalization, or

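### Intraoperative screen failures count in the safety population, but the protocol's rules on recording their post-operative adverse events conflict and set no observation window, so the 6-month AE rate can be biased low

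*Combined protocol and SAP*

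**What the plan says.** Section 3.3.3 covers a consented subject whose implant procedure has begun but who does not meet the intraoperative criterion. That subject is not implanted "and will be managed according to section 3.3.2".

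Section 3.3.2 is written for subjects who do not undergo the procedure. It says that AEs from consent "to the point of screen failure will be recorded, but no further follow-up will be required". It adds that events still open are followed until closed or judged chronic.

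The analysis sections count these subjects for safety. Section 5.2.3.1: "Adverse event data will be based on all implanted subjects and intra-operative screen failures". Section 5.2.3.2: "All safety data will be summarized and analyzed based on all implanted subjects and intraoperative screen failures".

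The general AE rules are broader. Section 8.6.1 says that any AE after consent, "whether before, during or subsequent to the procedure, must be recorded in the eCRF". Section 8.11 has the investigator monitor AEs in each enrolled subject, and 3.3.1 defines enrollment by signed consent, so intraoperative failures are included.

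On the endpoint, 5.2.4.1 states: "The primary safety endpoint of the study is the rate of adverse events (AEs) through 6-months". The synopsis words it as "Rate of adverse events (AEs) at 6 months post-activation".

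**The concern.** For an intraoperative failure, the point of screen failure falls during the operation. By then the subject has had anesthesia or sedation, and needle and lead placement have been attempted (4.1.2). Section 6.1 lists infection, hematoma, nerve injury and site pain among the risks, and these can appear after the subject leaves the operating room. Section 8.9 treats implant-site pain up to 30 days after the procedure as procedure-related, so the protocol itself expects procedure effects well after surgery.

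Section 3.3.4 gives the visit schedule to implanted subjects only. A site that follows 3.3.3 and 3.3.2 as written may record nothing new once the operation is abandoned, while a site that follows 8.6.1 records whatever it learns. Ascertainment can then differ between sites, and a subject who was not observed after surgery counts as event-free in a 6-month rate.

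At stake are the primary safety rate and the tabulation of adverse procedure effects (APEs) promised in 1.4. The direction matters. For effectiveness, 5.2.4.6.1 counts these subjects as treatment failures, which works against the device. For safety, counting them without observing them works in its favor.

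**Working it through.** **The rules side by side**

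- Recording: 3.3.2, applied through 3.3.3, sets the end of AE recording at screen failure. Section 8.6.1 extends recording past the procedure, and 8.11 extends monitoring to all enrolled subjects.
- Follow-up: implanted subjects have the full schedule. Intraoperative failures have no required contact; only events already open are followed.
- Denominator: both groups (5.2.3.1, 5.2.3.2).
- Time origin: activation, in the synopsis. An intraoperative failure has no activation date, so the six-month window is undefined for that subject.

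**The only figure in the plan that bounds the group**

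Section 5.2.2 assumes 20% attrition between enrollment and implant, from all screen failures and withdrawals together. 116 / (1 − 0.20) = 145, which reproduces the enrollment cap. At the cap, 145 − 116 = 29 subjects are lost before or at implant. The number lost intraoperatively is not given.

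**Size of a possible bias**

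Let

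- p = proportion of the 116 implanted subjects with at least one AE
- m = number of intraoperative failures (assumed)
- q = proportion of those failures with an AE starting after the point of failure and none recorded before it (assumed 5% to 20%)

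Events recorded before failure appear in both rates below and cancel, so they are left out.

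True rate = (116p + mq) / (116 + m)

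Recorded rate if no post-failure AE is captured = 116p / (116 + m)

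Difference = mq / (116 + m), which does not depend on p.

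For example, m = 5 and q = 0.20 gives 1.00 / 121 = 0.83 percentage points; m = 1 and q = 0.05 gives 0.05 / 117 = 0.04 points.

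| m | q = 5% | q = 10% | q = 20% |
|---|---|---|---|
| 1 | 0.04 | 0.09 | 0.17 |
| 3 | 0.13 | 0.25 | 0.50 |
| 5 | 0.21 | 0.41 | 0.83 |
| 29 (ceiling) | 1.0 | 2.0 | 4.0 |

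Entries are percentage points by which the recorded rate falls short. The last row assumes that every planned pre-implant loss happened in the operating room, which is implausible and serves only as a bound. With full capture, every entry is zero.

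**The case against.** The strongest reply is that the duty to record exists. Sections 8.6.1 and 8.11, with 3.3.1, reach post-procedure events in every consented subject. Open events are followed. Section 4.1.2 leaves post-operative wound care to the physician's usual practice, so the investigator has a route by which to learn of complications. Section 3.3.2 says only that further follow-up is not required; it does not forbid recording.

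This stands against three stronger readings that a reader might take from the text.

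- That no post-operative event in this group is captured. The general rules require such events to be recorded, so a capture of nil is a worst case and not something the documents establish.
- That the rules are impossible to follow together. A site could hold no study visits, report what it hears, and count the subject for safety. What remains is a conflict over when recording ends, and reliance on passive reporting. Keeping the original AE forms in the center's file does not rule out database entry either.
- That the rate is multiplied by 116/(116 + m), for instance 116/119 = 0.975 with three failures. That needs these subjects to contribute no events at all, although 3.3.2 records events up to failure. It also needs never-implanted subjects to carry the same six-month risk as implanted ones. The documents support neither.

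It is also fair to say that the primary safety endpoint carries no hypothesis or performance goal, that 1.4 tabulates event counts, which a larger denominator does not dilute, and that including everyone who had the procedure started is a defensible safety set. Section 5.2.2 says that all subjects were already enrolled and implanted by Rev F, so a new prospective contact comes largely too late.

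None of this supplies an observation window, removes the conflict between 3.3.2/3.3.3 and 8.6.1/8.11, or gives the six-month rate a meaning for subjects who were never activated.

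**Conclusion.** The point holds as an inconsistency with a likely, but not established, downward bias. The recording rules for intraoperative screen failures conflict, and the group sits in the denominator of a rate for which it has neither a time origin nor scheduled observation.

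The documents give neither the number of such subjects nor their post-operative AE risk, so the size cannot be computed. For 1 to 5 subjects, a risk of 5% to 20% and no capture, the rate would be understated by 0.04 to 0.83 percentage points; the ceiling of 29 gives 1.0 to 4.0. The effect on the overall rate is probably small and no test depends on it. The more important loss is descriptive: harms after an abandoned placement may go unreported. Because the remedy is specific and cheap, the change should be made.

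**What to change.** 1. In 3.3.3, replace the cross-reference to 3.3.2 with a separate AE-recording rule, consistent with 8.6.1 and 8.11: AEs in intraoperative screen failures go into the eCRF from consent through a stated post-procedure window. The sponsor should choose and justify its length; the 30 days already used in 8.9 to classify pain is one reference point.
2. For subjects already enrolled, collect these events retrospectively from site records over the same window, and document how far each record reaches.
3. In 5.2.3.1 and 5.2.3.2, tabulate APEs in all subjects with a procedure initiated and report the 6-month post-activation AE rate in implanted subjects. List intraoperative failures separately with their events and actual length of observation.
4. Use one time origin for the primary safety endpoint in the synopsis and 5.2.4.1.

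The cost is a protocol wording change, a small record query at the sites concerned, and a revised layout of the safety tables. The stated AE rate may rise slightly. Records may be incomplete for some subjects; showing the actual observation time makes that visible.
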